### 7.7.2. Coding of Therapies

All therapies are coded using WHO-DRUG. In the table(s), the generic term will be used. Multiple records of the same generic term for the same subject with the same categorization will be counted only once. The table will therefore present subjects, not occurrences.

### 7.7.3. Analysis

#### **Table 14.1.3.17: Prior therapies: Frequency table**

Frequency tabulation per treatment group (and overall) of the ATC classes and generic terms, of "prior" and "prior+concomitant" therapies only.

These are all the therapies that were used before the first intake of study medication.

Population: safety.

#### **Table 14.1.3.18: Concomitant therapies up to Week 12: Frequency table**

Frequency tabulation per treatment group (and overall) of the ATC classes and generic terms, selecting both "concomitant" (with a start date during the first study period, or a missing start date) and "prior+concomitant" (all of them) therapies.

These are all the therapies that were used during the first 12 weeks of the study, concomitantly to the study medication.

Population: safety.

#### **Table 14.1.3.19: Concomitant therapies over the whole study period: Frequency table**

Frequency tabulation per treatment group (and overall) of the ATC classes and generic terms, selecting "concomitant" and "prior+concomitant" therapies only.

These are all the therapies that were used during the study, concomitantly to the study medication.

Population: safety.

#### **Table 14.1.3.20: Post-treatment therapies: Frequency table**

Frequency tabulation per treatment group (and overall) of the ATC classes and generic terms, selecting "post-treatment" therapies only.

These are all the therapies that were used during the study, but started after the last dose of study medication.

Population: safety.

#### **Listing 16.2.4.5: Prior and concomitant therapies**

Listing per treatment group and per subject of all data on prior and concomitant therapies. Flags for prior/concomitant/post-treatment will be added. In case the therapy was due to an AE, the AE preferred term will be mentioned in this listing.

Population: safety.

## 7.8. EXPOSURE TO STUDY MEDICATION AND COMPLIANCE

### 7.8.1. Derivations for placebo/GLPG0634

For the first period of the study (baseline – Week 12):

- Total treatment duration (days) = (last dose administration date – first dose administration date) + 1 day, where the last dose administration date is cut off on the day prior to the Week 12 visit. (“Prior to the Week 12 visit”, because at the Week 12 visit the re-randomization takes place and it is not known when exactly on that day the new study drug is being taken.)
- Total treatment duration, excluding days off drug (days): sum of all durations (last – first +1) in the drug log pages where there is a morning and/or evening dose >0 capsules, and where the last duration is cut off on the day prior to the Week 12 visit.
- Percentage days with an intake =  $100\% \times \left( \frac{\text{total treatment duration, excluding days off drug}}{\text{total duration}} \right)$
- Total compliant treatment duration (days): sum of all durations (last – first +1) in the drug log pages where there is a morning and/or evening dose with exactly 2 capsules, and where the last duration is cut off on the day prior to the Week 12 visit.
- Percentage compliance =  $100\% \times \left( \frac{\text{total compliant treatment duration}}{\text{total duration}} \right)$

The “total duration” used as denominator in the above formulae equals: (date of Week 12 visit) – (date of first drug intake). This total duration is not including the Week 12 visit itself, just like the above derivations, because of the treatment switch happening at Week 12 making it uncertain which drug intakes actually happened at the day of the visit itself.

For the total 24 weeks study period:

- Total treatment duration (days) = (last dose administration date – first dose administration date) + 1 day.
- Total treatment duration, excluding days off drug (days): sum of all durations (last – first +1) in the drug log pages where there is a morning and/or evening dose >0 capsules.
- Percentage days with an intake =  $100\% \times \left( \frac{\text{total treatment duration, excluding days off drug}}{\text{total duration}} \right)$
- Total compliant treatment duration (days): sum of all durations (last – first +1) in the drug log pages where there is a morning and/or evening dose with exactly 2 capsules.
- Percentage compliance =  $100\% \times \left( \frac{\text{total compliant treatment duration}}{\text{total duration}} \right)$

### 7.8.2. Tables up to Week 12

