#### **8.5 Investigational Products.**

##### **8.5.1 Investigational Products Administered**

The study medication will consist of 25, 50 and 100 mg capsules of GLPG0634 for oral administration or matching placebo.

The following doses will be evaluated:

- GLPG0634 25 mg b.i.d.: 1 capsule of 25 mg GLPG0634 and 1 placebo capsule both in the morning and in the evening.
- GLPG0634 50 mg q.d.: 1 capsule of 50 mg GLPG0634 and 1 placebo capsule in the morning and 2 placebo capsules in the evening.
- GLPG0634 50 mg b.i.d.: 1 capsule of 50 mg GLPG0634 and 1 placebo capsule both in the morning and in the evening.
- GLPG0634 100 mg q.d.: 1 capsule of 100 mg GLPG0634 and 1 placebo capsule in the morning and 2 placebo capsules in the evening.
- GLPG0634 100 mg b.i.d.: 1 capsule of 100 mg GLPG0634 and 1 placebo capsule both in the morning and in the evening.
- GLPG0634 200 mg q.d.: 2 capsules of 100 mg GLPG0634 in the morning and 2 placebo capsules in the evening.
- Placebo: 2 placebo capsules both in the morning and in the evening.

At Week 12, subjects on placebo who have not achieved a 20% improvement in SJC66 and TJC68 will be re-randomized (automatically via IXRS) to treatment to receive GLPG0634 100 mg q.d. or 50 mg b.i.d. doses in a blinded fashion, subjects on 50 mg q.d. who have not achieved a 20% improvement in SJC66 and TJC68 will be assigned to 100 mg q.d. and subjects on 25 mg b.i.d. who have not achieved a 20% improvement in SJC66 and TJC68 will be assigned to 50 mg b.i.d. All will continue the study until Week 24. Subjects in the other groups will maintain their randomized treatments until Week 24.

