### **8.5.6 Selection and Timing of Dose for Each Subject**

The study medication will be administered with a glass of water daily in the morning and in the evening.

Each subject's dose will be selected by random allocation according to randomization procedures.

If a subject misses a dose (e.g., because he/she forgot to take the medication), he/she should take the missed dose within 5 hours after the planned intake time. If the study medication is not taken within 5 hours after the planned time, the missed dose should be skipped. For each dose taken, the number of capsules taken should be recorded on the subject's diary card. Additional to the number of capsules taken, the date and time of the very first intake, and for selected visits, the 2 most recent intakes prior to the visits will be recorded on the subject's diary card. For the methotrexate, the date and time for the most recent intake prior to the selected visits will be captured on the subject's diary card. During each visit, the investigator will record a summary of the study medication intake data in the eCRF.

Dose reduction during the study is not allowed. Instead, the subject should either temporarily stop all intake or permanently stop study medication. Every effort should be made to contact the medical monitor before stopping study medication (temporarily or permanently).

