### **8.5.10 Subject Diary Card**

Subjects will record any changes in concomitant illnesses, new AEs and any change in concomitant medication in their diary cards. Adverse events and changes in concomitant medication will be transcribed into the eCRF by the investigator. Details of dosing with study medication will be recorded in the subject diary and summarized in the eCRF by the investigator.

---

The subject diary card will be considered source information. The data from the subject diary card will not be entered into the study database.

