#### **8.8.1.1 Datasets or Populations Analyzed**

All randomized subjects who received at least one dose of study medication and have at least one post-Baseline efficacy assessment will be included in the efficacy analysis (intent-to-treat [ITT]).

A secondary per-protocol analysis will be performed to confirm the ITT analysis, excluding subjects with major protocol deviations (such as Baseline CRP within normal range, Baseline TJC68 <8, Baseline SJC66 <6, <80% study medication compliance, or use of forbidden concomitant medications). Full details of the major protocol deviations will be described in the statistical analysis plan, with adherence to analysis sets agreed upon prior to database lock and unblinding.

All randomized subjects who received at least one dose of study medication will be included in the safety analysis.

All randomized subjects who received at least one dose of GLPG0634 and who have at least one PK measurement will be included in the PK analysis.

Reasons for study termination will be tabulated.

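### As written, the SAP compliance percentage ignores a missed morning or evening intake, and the average weekly methotrexate dose to Week 12 is exactly 7 times too high

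*SAP*

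**What the plan says.** **Study drug.** Protocol 8.5.1 gives every arm two capsules in the morning and two in the evening. In the 200 mg q.d. arm this is "2 capsules of 100 mg GLPG0634 in the morning and 2 placebo capsules in the evening"; in the 100 mg b.i.d. arm it is "1 capsule of 100 mg GLPG0634 and 1 placebo capsule both in the morning and in the evening". Protocol 8.5.6 foresees single missed intakes: "If the study medication is not taken within 5 hours after the planned time, the missed dose should be skipped".

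SAP 7.8.1 defines the compliant duration as the sum of the log-line durations "in the drug log pages where there is a morning and/or evening dose with exactly 2 capsules", for the first 12 weeks and again for the 24 weeks. Percentage compliance is that sum over a total duration, defined as the Week 12 visit date minus the date of first intake: "This total duration is not including the Week 12 visit itself, just like the above derivations". No total duration is given for the 24-week percentage, or for a subject who has no Week 12 visit. Table 14.1.4.1 sorts the percentage into classes that include 100–120% and above 120%.

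**Methotrexate.** SAP 7.9.1 notes that the eCRF holds weekly doses. It defines total dose as the number of days on each log line times the weekly dose, from Screening to the Week 12 visit. It divides that by the inclusive days from Screening to Week 12, over 7. For the 24 weeks the numerator again starts at Screening, but the denominator runs from the Week 12 visit to the Week 24, follow-up or early discontinuation visit. Table 14.1.4.4 uses the classes below 10, 10 to 15, above 15 to 20, and above 20 mg/week.

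**The concern.** The compliance rule accepts either intake, while the prescription requires both. It cannot be rescued by reading its and/or as and: the preceding bullet in SAP 7.8.1 uses the same construction for days with any intake at all, where it must mean either one.

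The gap matters because capsules are not interchangeable across arms. By Protocol 8.5.1, a skipped morning intake in a q.d. arm loses all of that day's active drug, and a skipped evening intake loses none. In a b.i.d. arm either one loses half. The SAP percentage gives all these days full marks if the other intake was two capsules, so it says little about adherence behind the exploratory q.d. versus b.i.d. comparison.

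Protocol 8.8.1.1 also lists "<80% study medication compliance" as a major deviation for the per-protocol set. If that cut-off is applied to this derivation, subjects who missed a large share of their capsules would stay in.

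For methotrexate, days times mg/week is never converted to mg, so the table would not show whether background therapy stayed at its entry level.

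**Working it through.** The documents print no result for these derivations, so there is no figure to reproduce. The formulas are applied as written.

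**Compliance to Week 12**

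Inputs: 2 + 2 capsules a day (Protocol 8.5.1); first intake on Day 1 and Week 12 visit on Day 85 (Protocol 8.6.2.5), so the denominator is 85 − 1 = 84 days and 336 capsules are scheduled. Missed intakes are assumed to be visible in the log.

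| Pattern over 84 days | SAP rule | Days with 2 + 2 | Capsules taken / 336 |
|---|---|---|---|
| All mornings taken, 17 evenings missed | 84/84 = 100% | 67/84 = 79.8% | 302/336 = 89.9% |
| All mornings taken, 34 evenings missed | 100% | 50/84 = 59.5% | 268/336 = 79.8% |
| All mornings taken, 84 evenings missed | 100% | 0% | 168/336 = 50.0% |
| 2 morning + 1 evening every day | 100% | 0% | 252/336 = 75.0% |
| 68 morning-only days, 16 days off | 68/84 = 81.0% | 0% | 136/336 = 40.5% |

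Mirror case, k mornings missed and all evenings taken: the SAP rule gives 100%. Active drug received is (84 − k)/84 in a q.d. arm and (168 − k)/168 in a b.i.d. arm. For k = 34 that is 59.5% and 79.8%; for k = 84 it is 0% and 50%.

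Classes above 100%: if no date is counted on two log lines, the numerator cannot exceed 84, so these classes stay empty. One double-counted day gives 85/84 = 101.2%; passing 120% needs 17 of them (101/84 = 120.2%).

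**Methotrexate to Week 12**

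Let d be the days and w the weekly dose on each log line, and T the inclusive days from Screening to Week 12.

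- SAP: Σ(d × w) / (T/7) = 7 × Σ(d × w)/T.
- Time-weighted mean weekly dose: Σ(d × w)/T.

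The ratio is 7 for any dosing history, because both parts cover the same window.

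- Constant doses of 10, 15, 20 and 25 mg/week print as 70, 105, 140 and 175.
- 20 mg/week for 57 days, none for 14 days, then 15 mg/week for 43 days (T = 114): (1140 + 645)/114 = 15.66 true, 109.6 by the SAP.
- The class limits 10, 15 and 20 correspond to true averages of 1.43, 2.14 and 2.86 mg/week. Every constant dose allowed by Protocol 8.3.2 (10 to 25 mg/week) falls in the top class.

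**Methotrexate over 24 weeks**

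Take Week 12 on Day 85 and Week 24 on Day 169, so the denominator is 84/7 = 12.

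- Literal reading, Screening on Day −2: 171 days, factor 171/12 = 14.25.
- Literal reading, Screening on Day −29: 198 days, factor 198/12 = 16.5. A constant 15 mg/week prints as 213.75 to 247.5 across the two screening days.
- With visit windows of ±2 days and an end date at Week 24 or at follow-up 7 to 10 days later: 7 × 183/98 = 13.07 to 7 × 196/80 = 17.15.
- Early discontinuation soon after Week 12 gives more. For a visit on Day 113: 7 × 115/28 = 28.75 to 7 × 142/28 = 35.5.
- If a second-period average was meant, with the numerator limited to that period: 84/12 = 7.0, or 85/12 = 7.08 if the Week 12 day is included.

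**The case against.** The strongest reply concerns reach. The affected outputs are descriptive tables without p-values: 14.1.4.1, 14.1.4.2, 14.1.4.4 and 14.1.4.6, and the derived-data Listings 16.2.5.2 and 16.2.5.5. None is marked for the Week 12 interim analysis that supports phase III dose selection. A printed 105 mg/week of methotrexate would be noticed at once, and the Week 12 values can be recovered by dividing by 7. The dose-change tables, the starting-dose table and the eCRF listings are correct. All of this stands and limits the severity. It does not make the formulas right: a programmer who follows the SAP prints wrong numbers, and one who corrects them silently departs from it. The 24-week methotrexate figures, read literally, have no common factor to divide out.

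The per-protocol link is unproven. SAP 2.1.1 leaves exclusions to the blind review meeting, and SAP 7.2 refers to a Protocol Deviation Plan that is not among the documents. That stands.

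The compliance examples depend on a log layout that is not shown. Protocol 8.5.6 says "the investigator will record a summary of the study medication intake data in the eCRF", and Protocol 8.5.10 says "The data from the subject diary card will not be entered into the study database". If scattered misses are not logged as separate lines, no rule applied to the log would find them. If morning and evening sit on separate lines, dates could count twice and the classes above 100% could fill. This too stands as a limit on the examples.

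Finally, the SAP percentage is not blind to everything. It falls for full days off drug and for days when neither intake is exactly two capsules.

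**Conclusion.** Both errors hold on the text, and no other section corrects them. The methotrexate factor of 7 to Week 12 is algebra and needs no assumption beyond the subject having a Week 12 date. The 24-week methotrexate formula is wrong on either reading: the whole study, as the title of Table 14.1.4.6 suggests, or a second-period average, as the opening of SAP 7.9.1 suggests. The compliance percentage can read 100% with half of the capsules missed, provided the log records intakes in enough detail to show it. The undefined denominators alone would be missing detail; the other two points are errors. This should be fixed. It does not bear on the primary ACR20 analysis with non-responder imputation.

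**What to change.** **Compliance.** Choose one:

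- Count a day as compliant only with exactly two capsules in the morning and exactly two in the evening, and drop the classes above 100%.
- Use capsules taken / (4 × days), with morning and evening percentages shown separately. The split is needed because a pure count lets doubled and skipped intakes cancel: four capsules every morning and none in the evening gives 336/336 = 100%, but 200% and 0% when split. It also separates the q.d. and b.i.d. cases, which a total count does not.

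Define the total duration for the 24-week percentage and for subjects who stop without a Week 12 visit, for example up to the date of discontinuation. State whether the per-protocol 80% cut-off uses this variable.

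**Methotrexate.** Average weekly dose = Σ[(days/7) × weekly dose] / (days in period/7), with numerator and denominator over the same stated dates. Say whether the second value runs from Screening or from Week 12, and which end date applies when there is no Week 12 visit.

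**Cost.** SAP wording and table code. Probably no new data are needed, since the SAP already reads morning and evening capsules and weekly methotrexate doses from the log pages. Check first that the log separates days on which only one intake was missed.

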#### Table 14.1.4.1: Use of study medication up to Week 12: Descriptive statistics

Descriptive statistics per treatment group (and overall) of the total treatment duration (days) and the overall compliance (%).

Frequency tabulation per treatment group (and overall) of the two treatment duration parameters, categorized in weeks.

Frequency tabulation per treatment group (and overall) of the days with intake and compliance, categorized as:

<80% ;

[80%,100%[ ;

100% ;

]100%,120%] ;

>120%.

Population: safety.

### **7.8.3. Tables for the whole 24 weeks period**

#### **Table 14.1.4.2: Use of study medication over the whole study period: Descriptive statistics**

Similar to the preceding table, also using the 11 treatment sequences of Chapter 3.

### **7.8.4. Listings**

#### **Listing 16.2.5.1: Exposure to study medication: eCRF data**

Listing per treatment group and per subject of all data related to the use of study medication as recorded in the eCRF.

Population: safety.

#### **Listing 16.2.5.2: Exposure to study medication: Derived data**

Listing per treatment group and per subject of all derived parameters related to the use of study medication.

Population: safety.

#### **Listing 16.2.5.3: Dispensed kit numbers**

Listing per treatment group and per subject of all dispensed placebo/GLPG0634 kit numbers, flagging any mistakes in dispensing.

Population: safety.

## 7.9. EXPOSURE TO METHOTREXATE AND COMPLIANCE

### 7.9.1. Derivations for methotrexate

The average weekly dose (mg) of methotrexate (MTX) in each of the two study periods is derived from summing up the durations of loglines with a weekly dose >0. The eCRF collects the use of MTX in terms of total weekly doses rather than daily doses.

For the first period of the study (screening – Week 12):

- MTX dose change: decrease / no change / increase: at any time during the entire period, versus the dose used at the start of the study.
- Total dose, excluding days off drug (days): sum of all doses (*last – first + 1*) x (*weekly dose in that period*) in the MTX drug log pages where there is a weekly dose >0 mg, and where the first duration starts with the screening date and the last duration is cut off on the day of the Week 12 visit.

$$\text{Average weekly dose (mg)} = \frac{\text{total dose}}{(\text{date of Week 12} - \text{date of screening} + 1) / 7}$$

For the whole 24 weeks study period:

- MTX dose change: decrease / no change / increase: at any time during the entire period, versus the dose used at the start of the study.
- Total dose, excluding days off drug (days): sum of all doses (*last – first + 1*) x (*weekly dose in that period*) in the MTX drug log pages where there is a weekly dose >0 mg, and where the first duration starts with the screening date and the last duration is cut off on the day of the Week 24/FU/Early discontinuation visit (whichever applies).

$$\text{Average weekly dose (mg)} = \frac{\text{total dose}}{(\text{date of Week 24/FU/Early term visit} - \text{date of Week 12}) / 7}$$

### 7.9.2. Tables up to Week 12

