#### **8.6.2.5 Week 12 (Visit 7)**

The Week 12 visit (Visit 7) will take place on Day 85 ± 2 calendar days relative to the start of study medication intake.

- Any remaining study medication as well as empty study medication containers will be returned to the investigator and an accountability check will be performed.
- Any AEs that have occurred since signing the ICF will be documented, and any changes in concomitant medication will be reported.
- Vital signs will be measured.
- A 12-lead ECG will be performed.
- A physical examination will be performed.
- The subject diary card will be collected, a summary will be recorded in the eCRF, and a new subject diary card will be dispensed.
- Blood samples for measurement of PK and PD parameters will be collected.
- Serum CRP will be measured.
- SJC66 and TJC68 evaluations will be performed.
- Physician's and Patient's Global Assessments of Disease Activity will be completed.
- The subject will complete the HAQ-DI.
- The subject will complete the FACIT fatigue scale and the SF-36 questionnaire.
- Hematology, clinical chemistry, and urinalysis (dipstick and microscopy) tests will be performed on samples collected at this visit. A urine pregnancy test will be performed on females of childbearing potential.

CONFIDENTIAL

At visit 7, subjects on placebo who have not achieved a 20% improvement in SJC66 and TJC68 will be re-randomized (automatically via IXRS) to treatment to receive GLPG0634 100 mg q.d. or 50 mg b.i.d. doses in a blinded fashion, subjects on 50 mg q.d. who have not achieved a 20% improvement in SJC66 and TJC68 will be assigned to 100 mg q.d. and subjects on 25 mg b.i.d. who have not achieved a 20% improvement in SJC66 and TJC68 will be assigned to 50 mg b.i.d. All will continue the study until Week 24. Subjects in the other groups will maintain their randomized treatment until Week 24.

When all of these procedures have been performed, the study medication will be dispensed according to the information provided using IXRS and the date of the next visit confirmed.

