#### **8.6.3 Follow-up (Visit 11)**

A Follow-up visit (Visit 11) will be performed only for subjects discontinuing prematurely from the study and for subjects not entering the Long Term Follow-up Study GLPG0634-CL-205. This will take place 7 to 10 calendar days after either the EDV or the Week 24 visit.

- Any AEs that have occurred since signing the ICF will be documented, and any changes in concomitant medication will be reported.
- Vital signs will be measured.
- A 12-lead ECG will be performed.
- A physical examination will be performed.
- Hematology, clinical chemistry, and urinalysis (dipstick and microscopy) tests will be performed on samples collected at this visit. A urine pregnancy test will be performed on females of childbearing potential.

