**Table 14.1.4.5: Changes in methotrexate over the whole study period: tabulation**

**Table 14.1.4.6: Use of methotrexate over the whole study period: Descriptive statistics of the average weekly dose**

### **7.9.4. Listings**

**Listing 16.2.5.4: Exposure to methotrexate: eCRF data**

Listing per treatment group and per subject of all data related to the use of methotrexate, as recorded in the eCRF.

Population: safety.

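### SAP 7.9.1 overstates the average weekly MTX dose 7-fold up to Week 12 and by a varying factor over 24 weeks; SAP 7.5.1 gives RA duration the wrong sign

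*SAP*

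**What the plan says.** **MTX up to Week 12 (SAP 7.9.1).** On the unit of dose: "The eCRF collects the use of MTX in terms of total weekly doses rather than daily doses". The numerator is the "sum of all doses (*last – first + 1*) x (*weekly dose in that period", taken over log lines with a positive dose from screening to the Week 12 visit. The denominator is the inclusive number of days from screening to Week 12, divided by 7. Table 14.1.4.4 reports the result in mg/week, with cut-offs at 10, 15 and 20.

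**MTX over 24 weeks (SAP 7.9.1).** The numerator is the same product, where "the first duration starts with the screening date and the last duration is cut off on the day of the Week 24/FU/Early discontinuation visit", followed by a whichever-applies clause. The denominator is the date of that end visit minus the Week 12 date, divided by 7. The result goes into "Table 14.1.4.6: Use of methotrexate over the whole study period: Descriptive statistics of the average weekly dose". The opening sentence of 7.9.1, however, says the average weekly dose "in each of the two study periods is derived from summing up the durations of loglines" with a positive dose.

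**RA duration (SAP 7.5.1).** This is the diagnosis date minus the screening date, plus 1, over 365.25, rounded to an integer. MTX duration in the same list is subtracted the other way round: screening date minus start date.

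**The concern.** The units do not cancel in the MTX formulas. Days times mg/week, divided by weeks, is not mg/week; it is 7 times that. The 24-week version has a second fault, because numerator and denominator cover different spans. Its error therefore depends on screening length, on which end visit is used and on when the subject leaves, so treatment sequences with different late dropout would show different average MTX doses even on identical MTX. Neither average is defined for a subject without a Week 12 date.

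RA duration cannot be right as written, since Protocol 8.3.2 requires the diagnosis to precede screening by at least 6 months.

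At stake is the description of background MTX in an add-on-to-MTX trial, and the RA-duration rows of Table 14.1.3.7 (repeated by region and by responder status in 14.1.3.8 and 14.1.3.9) and of the ACR20 and DAS28(CRP) subgroup Tables 14.2.1.1.10 and 14.2.1.4.7.

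**Working it through.** The documents print no numerical result for these formulas, so there is no figure to reproduce. The check applies the formulas literally to the protocol's visit days.

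**Inputs**
- Screening on Day -29 to Day -2 (Protocol 8.6.1.1).
- Week 12: "The Week 12 visit (Visit 7) will take place on Day 85 ± 2 calendar days" (Protocol 8.6.2.5). Week 24: Day 169 ± 2 (8.6.2.8). Weeks 16 and 20: Days 113 and 141.
- Follow-up: "This will take place 7 to 10 calendar days after either the EDV or the Week 24 visit" (Protocol 8.6.3).
- There is no Day 0 (SAP 3.1), so Day -s to Day e inclusive is s + e days.
- Permitted stable MTX dose: 15 to 25 mg/week, or 10 in case of intolerance (Protocol 8.3.2).

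**1. Up to Week 12, dose D mg/week.** Printed value = (days × D) / (days / 7) = 7D.
- Screening Day -29: 29 + 85 = 114 days; (114 × 15) / (114 / 7) = 105.
- Screening Day -2: 2 + 85 = 87 days; (87 × 15) / (87 / 7) = 105.
- With 14 days off drug at 15 mg/week and screening on Day -29, the true average is 13.158 and the printed value 92.105, again a factor of 7.
- Doses of 10, 15, 20 and 25 print as 70, 105, 140 and 175. A printed value of 20 or less needs a true average of at most 20 / 7 = 2.86 mg/week.

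**2. Over 24 weeks, constant dose.** Factor = (s + e) / ((e − Week 12 day) / 7). Ranges run over the screening days and, where follow-up is the end date, over the 7 to 10 days.

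| Case | End date | Largest | Smallest |
|---|---|---|---|
| Completer, nominal days | Week 24 (Day 169) | 198/12 = 16.5 | 171/12 = 14.25 |
| Completer, nominal days | Follow-up (Day 176 to 179) | 205/13 = 15.8 | 181/13.43 = 13.5 |
| Completer, ±2-day windows | Week 24 | 196/(80/7) = 17.2 | 173/(88/7) = 13.8 |
| Completer, ±2-day windows | Follow-up | 203/(87/7) = 16.3 | 183/(98/7) = 13.1 |
| Exit at Week 20 | Early discontinuation visit (Day 141) | 170/8 = 21.3 | 143/8 = 17.9 |
| Exit at Week 20 | Follow-up (Day 148 to 151) | 177/9 = 19.7 | 153/9.43 = 16.2 |
| Exit at Week 16 | Early discontinuation visit (Day 113) | 142/4 = 35.5 | 115/4 = 28.75 |
| Exit at Week 16 | Follow-up (Day 120 to 123) | 149/5 = 29.8 | 125/5.43 = 23.0 |

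For a completer at nominal days with Week 24 as end date, 15 mg/week prints as 214 to 248. Removing only the factor 7 leaves 14.25 / 7 = 2.04 to 16.5 / 7 = 2.36.

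With a dose change (15 mg/week to Week 12, then 20; screening Day -29, end Day 169), the SAP formula gives (114 × 15 + 84 × 20) / 12 = 282.5. The whole-period average is 3390 / 198 = 17.12; the average after Week 12 is 20.

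**3. RA duration.**
- Diagnosis 5 years (1826 days) before screening: (−1826 + 1) / 365.25 = −5.00.
- Diagnosis 6 months (183 days) before: (−183 + 1) / 365.25 = −0.50, which is 0 after rounding.

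Every eligible subject therefore falls in the lowest class: <0.5 years in SAP 7.5.1, <1 year in the subgroup tables.

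**The case against.** The best defence concerns the 24-week figure. The opening of 7.9.1 speaks of each of the two periods, 7.9.2 asks for Table 14.1.4.4 per study period, and 7.9.3 calls the 24-week tables similar. If a period-2 average was meant, the denominator is right for a count starting the day after Week 12. The only extra fault is then a screening start carried over into the numerator, and correcting it leaves a constant factor of 7. This reading is plausible, so the ranges above measure the literal formula, not a settled intention. It does not rescue the text, because the heading, the numerator and the table title all say the whole period.

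Two limits also stand. The factor of 7 applies only to subjects with a Week 12 date, and SAP 3.3 places early discontinuation visits on Days 71 to 98 in the Week 12 window. Whether 7.9.1 uses that window is not said, so the undefined group may be smaller than it first appears. The whichever-applies clause does not settle the end date for a subject who has both a Week 24 or early discontinuation visit and a follow-up visit.

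On impact, a dose of 105 mg/week or a negative disease duration would be noticed at first output. The RA-duration tables were due at the Week 12 interim, yet the later corrections in SAP 6.3.2 mention no such problem. That suggests the code may have followed the evident intention, but does not prove it. The mock tables are a separate document that was not available. Code that silently departs from the SAP would itself be an undocumented deviation.

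**Conclusion.** All three formulas are wrong as written.

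- **Up to Week 12:** the average is exactly 7 times too high for any subject with a Week 12 date, whatever the screening length or days off drug.
- **Over 24 weeks:** at constant dose and taken literally, the factor is 13.1 to 17.2 for completers across both end dates and the visit windows. It rises the sooner after Week 12 a subject leaves, so no single divisor repairs Table 14.1.4.6.
- **Consequence:** every subject on a constant permitted dose for whom the average can be computed lands in the >20 mg/week class of Tables 14.1.4.4 and 14.1.4.6.
- **RA duration:** every eligible subject falls in the lowest class. In the exploratory models of Tables 14.2.1.1.11 and 14.2.1.4.8 the coefficient only changes sign, which inverts the odds ratio in the ACR20 model.

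The primary ACR20 analysis, the MTX dose-change tables (14.1.4.3, 14.1.4.5) and the starting-dose descriptive statistics (14.1.3.13) are not affected. This should be corrected, but it does not threaten the trial's main conclusion.

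**What to change.** - **Total MTX dose:** define it as the sum of (days × weekly dose / 7).
- **24-week average:** either divide by (end visit − screening + 1) / 7, or, if a period-2 average is meant, start the numerator the day after Week 12, keep the present denominator and relabel Table 14.1.4.6.
- **End dates:** use the last visit for subjects without a Week 12 visit. State which of Week 24, follow-up and early discontinuation visit counts when a subject has more than one.
- **RA duration:** define it as (screening date − diagnosis date + 1) / 365.25.

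The cost is SAP wording, a few lines of code and a check of any affected output already produced. With these changes a constant MTX dose returns itself, and a diagnosis 5 years before screening gives 5.
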